12.4 Discontinued Subjects

Subjects may be discontinued (exited) from the study early due to:

- ≠ Failure to meet protocol eligibility criteria prior to or during surgery
- ≠ Adverse event(s)
- ≠ Administrative reasons (eg, voluntary withdrawal, lost to follow-up)

Subjects who fail to meet protocol eligibility criteria prior to implantation will not be followed beyond the date of determination of ineligibility unless the reason for ineligibility is the occurrence of an adverse event. Subjects who are discontinued due to an adverse event occurring prior to implantation will be followed until resolution or stabilization of the event. Implanted subjects and subjects with failed implantation (inability to successfully deploy or insert the CyPass) will be followed until the planned end of study period.

Discontinued subjects who have been implanted or in whom implantation failed will not be replaced. Notification of a subject's early discontinuation should be made immediately to the sponsor and documented on the appropriate eCRF.

If a subject exits the study before completion of the final, planned study visit (Visit 8), the Investigator should make reasonable attempts to have the subject return to the site to perform early exit procedures. Early exit procedures are all study procedures to be conducted at Visit 8 (see Section 12.2.10).

12.5 Clinical Trial Termination

The Sponsor reserves the right to close the investigational site or terminate the study in its entirety at any time, for reasonable cause. The Investigator also may terminate the study at his/her site for reasonable cause. Reasons for the closure of an investigational site or termination of the study may include:

- ≠ The Investigator fails to comply with the protocol or GCP guidelines
- ≠ Safety concerns
- ≠ Inadequate recruitment of subjects by the Investigator

If the clinical study is prematurely terminated or suspended, the Sponsor will inform the Investigator and the regulatory authorities (where applicable) of the termination/suspension and the reason for the termination/suspension. The Investigator should promptly notify the IRB/IEC of the termination or suspension and the reasons.

If the Sponsor terminates the study for safety reasons, it will immediately notify the Investigator(s), and provide written instructions for study termination and applicable subject follow-up.

13 DEVICE DEFICIENCIES AND ADVERSE EVENTS

13.1 General Information

An AE is any untoward medical occurrence, unintended disease or injury, or untoward clinical signs (including abnormal laboratory findings) in subjects, users, or other persons, whether or not related to the investigational medical device (test article). Refer to the Glossary of Terms for categories of AEs, ADEs, and SAEs.

Figure 13-1 Categorization of All Adverse Events

[figure not shown]
[figure not shown]

Figure 13–2

Categorization of All Serious Adverse Events

13.1.1 **Intraoperative Adverse Events**

Anticipated intraoperative adverse events include, but are not limited to, the following cataract surgery and other intraoperative complications.

- a) Anterior capsule tear
- b) Choroidal detachment
- c) Posterior capsular rupture
- d) Vitreous in the anterior chamber
- e) Choroidal hemorrhage or effusion
- f) Cyclodialysis cleft – oversized
- g) CyPass non-implantation after penetration of the tissue plane between the ciliary body and the scleral spur
- h) Descemet's membrane break
- i) Hyphema obscuring the surgeon's view
- j) Inadvertent loss of vitreous not associated with the cataract procedure
- k) Inadvertent perforation of sclera
- l) Secondary ocular surgical intervention – AC lavage
- m) Significant corneal damage
- n) Significant iris injury or trauma
- o) Subconjunctival hemorrhage
- p) Zonular dialysis

13.1.2 Postoperative Adverse Events

Anticipated postoperative adverse events include, but are not limited to, the following complications.

- a) BCDVA loss of 2 lines (10 letters) or more on the ETDRS chart measured at or after 3 months postoperative compared to BCDVA at Visit 3 (1 Month Follow-up)
- b) Persistent (at time of study exit) BCDVA loss of 3 or more lines compared to best BCDVA achieved during the course of study
- c) 2-point worsening to severe on the slit lamp examination findings (other than cells and flare) at or after 3 months postoperative not associated with a pre-existing condition compared to Visit 0 (Screening)
- d) Endophthalmitis
- e) Flat AC with lens cornea touch
- f) Shallow AC with iridocorneal apposition
- g) Shallow AC with peripheral iridocorneal apposition
- h) Aqueous misdirection
- i) Anterior chamber cell and flare requiring either an increase in the standard protocol postoperative steroid regimen or initiation of steroid treatment following completion of the protocol postoperative steroid regimen
- j) Conjunctivitis
- k) Keratitis
- l) Corneal edema (mild to moderate corneal edema prior to 1 month postoperative is not considered an adverse event)
- m) Corneal opacification
- n) Corneal decompensation
- o) Persistent hyphema of >2 mm present greater than 1 day postoperative
- p) Retinal detachment
- q) Other retinal complications (eg, dialysis, flap tears, or proliferative vitreoretinopathy)
- r) Increase in C/D ratio of ≥ 0.3 units on slit lamp biomicroscopic examination
- s) Confirmed worsening in the visual field mean deviation (MD) of ≥ 2.5 dB compared to the MD used to determine subject eligibility
- t) Choroidal hemorrhage or choroidal effusion, defined as a choroidal effusion or detachment with at least a partially hemorrhagic component that obstructs vision or causes pain (including both peripheral and “kissing” choroidal detachments) lasting longer than 1 month
- u) Peripheral anterior choroidal effusion
- v) Maculopathy associated with hypotony
- w) Maculopathy associated with cystoid edema
- x) Hypotony (defined as IOP <6 mmHg) at or after 1 month postoperative

y) Clinically significant hypotony, defined as IOP <6 mmHg with any of the following findings:

- i. Maculopathy
- ii. Flat AC chamber requiring reformation
- iii. Corneal folds
- iv. Worsening of with-the-rule astigmatism by ≥ 1 diopter, or rotation of against-the-rule astigmatism to ≥ 1 diopter of with-the-rule astigmatism
- v. Choroidal effusion requiring surgical drainage
- vi. Suprachoroidal hemorrhage
- vii. BCDVA loss of ≥ 2 lines from the best postoperative BCDVA

z) Elevated mean IOP ≥ 10 mmHg than the qualifying baseline mean IOP at or after 1 month postoperative

aa) CyPass device obstructed by iris, vitreous, lens, fibrous overgrowth, fibrin, or blood

bb) CyPass device malposition – positioning after deployment such that the device is not in the supraciliary space

cc) CyPass device malposition – positioning after deployment such that there is a clinical sequela resulting from device position including, but not limited to:

- i. Secondary surgical intervention to modify device position (eg, repositioning, proximal end trimming or explantation)
- ii. Corneal endothelial touch by device
- iii. Corneal edema leading to loss of BCDVA > 2 lines at the last postoperative visit, in comparison with preoperative BCDVA
- iv. Progressive ECL, defined as ongoing reduction in endothelial cell count of 30% or more relative to the screening ECD value, where ‘ongoing reduction in endothelial cell count’ is defined as losses continuing after Visit 5 (6 Month Follow-up)
- v. Erosion of device through sclera
- vi. Device obstruction requiring secondary surgical intervention

dd) CyPass device dislodgement or movement, without sequelae, where device movement is defined as a change by at least 1 in the number of CyPass rings visible that is not attributable to variations in gonioscopic viewing angle or illumination, changes in angle anatomy due to concomitant findings such as resolution of hyphema, change in anterior chamber depth, or development of focal peripheral anterior synechiae

ee) CyPass device explantation associated with CyPass placement and stability

ff) CyPass device explantation NOT associated with CyPass placement and stability

gg) Unplanned ocular surgical reintervention associated with CyPass placement and stability

hh) Unplanned ocular surgical reintervention NOT associated with CyPass placement and stability (other than paracentesis to relieve pressure prior to 1 week postoperative or Nd:YAG capsulotomy)

- ii) Significant ptosis
- jj) Atrophy/phthisis
- kk) Wound dehiscence/leak (persistent aqueous leak or fistula formation)
- ll) Subconjunctival hemorrhage
- mm) Chronic pain in the study eye present greater than 3 months postoperative
- nn) Significant foreign body sensation at or after 3 months postoperative
- oo) IOL subluxation

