6 SCHEDULE OF VISITS

Procedure/Assessment	Visit 0 (-42 to -1 days) Screening	Visit 00 (Day 0) Surgery	Visit 1 (+1 day) 1 Day Follow-up	Visit 2 (+5 to 9 days) 1 Week Follow-up	Visit 3 (+21 to 35 days) 1 Month Follow-up	Visit 4 (+70 to 98 days) 3 Month Follow-up	Visit 5 (+150 to 210 days) 6 Month Follow-up	Visit 6 (+330 to 420 days) 12 Month Follow-up	Visit 7 (+690 to 780 days) 24 Month Follow-up	Visit 8 (+1050 to 1140 days) 36 Month Follow-up/Exit/Early Exit
Informed Consent	X									
Demographics	X									
Medical History	X	X	X	X	X	X	X	X	X	X
Concomitant Medications	X	X	X	X	X	X	X	X	X	X
Number of Ocular Hypotensive Medications	X ¹	X	X	X	X	X	X	X	X	X
Urine Pregnancy Test ²	X									
Inclusion/Exclusion	X									
Surgery ³ (with video)		X								
Manifest Refraction	X ¹			X	X	X	X	X	X	X
Monocular BCDVA	X ^{1,4}		X ⁵	X	X	X	X	X	X	X
Specular Microscopy ⁶	X ¹					X	X	X	X	X
Visual Field ⁷	X ¹							X	X	X
IOP (8:00 – 10:00 am)	X ¹		X	X	X	X	X	X	X	X
Slit Lamp Examination	X ¹		X	X	X	X	X	X	X	X
Gonioscopy (photographed)	X ¹	X	X	X	X	X	X	X	X	X
Fundus Examination	X ¹					X	X	X	X	X
Central Corneal Pachymetry	X ¹							X	X	X
UBM or OCT ⁸						(X)	(X)	(X)	(X)	(X)
Adverse Events	X	X	X	X	X	X	X	X	X	X
Device Deficiencies	X	X	X	X	X	X	X	X	X	X

¹ Conduct bilaterally at Visit 0 and in study eye only at postoperative visits, unless otherwise indicated.

² In women of child bearing potential only.

³ An Alcon observer may be present during surgery.

⁴ At Visit 0, if BCDVA better than 0.3 logMAR (> 85 letters read), repeat with BAT (Brightness Acuity Meter).

⁵ At Visit 1 (Day 1 Follow-up) BCDVA will be conducted as a pinhole test.

⁶ ECD may be requested in the fellow eye at follow-up on a case by case basis.

⁷ Visual field testing may be repeated between screening (Visit 0) and surgery (Visit 00), if needed.

⁸ UBM or OCT conducted if CyPass is not visible on Gonioscopy at two consecutive visits after Visit 3 (1 Month Follow-up). Images retained at site to demonstrate placement of CyPass.

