8.2.2 Safety Endpoints

8.2.2.1 Primary Safety Endpoint

The primary endpoint is the rate of clinically relevant complications associated with CyPass Micro-Stent placement and stability as determined at 36 months. Specific device-related complications include:

- ≠ Failure to implant CyPass, defined as inability to successfully deploy or insert the CyPass.
- ≠ Clinically significant CyPass malposition, defined as CyPass positioning after deployment such that:
 - The device is not in the supraciliary space, or
 - There is a clinical sequela resulting from device position including, but not limited to:
 - ≠ Secondary surgical intervention to modify device position (eg, repositioning, proximal end trimming or explantation)
 - ≠ Corneal endothelial touch by device
 - ≠ Corneal edema leading to loss of BCDVA > 2 lines at the last postoperative visit, in comparison with preoperative BCDVA
 - ≠ Progressive ECL, defined as ongoing reduction in endothelial cell count of 30% or more relative to the screening ECD value, where 'ongoing reduction in endothelial cell count' is defined as losses continuing after Visit 5 (6 Month Follow-up)
 - ≠ Erosion of device through sclera
 - ≠ Device obstruction requiring secondary surgical intervention.

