8.2.2.2 Secondary Safety Endpoints

All secondary safety endpoints will be evaluated at 36 months postoperatively.

- ≠ Rate of occurrence of sight-threatening adverse events including
 - Persistent (at time of study exit) BCDVA loss of 3 or more lines compared to best BCDVA achieved during the course of study
 - Endophthalmitis
 - Corneal decompensation
 - Retinal detachment
 - Severe choroidal hemorrhage or detachment
 - Aqueous misdirection
- ≠ The rate of ocular secondary surgical interventions (SSI)
- ≠ The rate of ocular SSIs associated with CyPass placement and stability

8.2.2.3

Other Safety Endpoints

All other safety endpoints will be evaluated at 36 months postoperatively.

- ≠ Increase from baseline IOP of 10 mmHg or greater at any time at/after 30 days postoperative
- ≠ BCDVA loss of 2 or more lines compared to screening (Visit 0)
- ≠ BCDVA loss of 2 or more lines in comparison with best recorded BCDVA at any postoperative visit
- ≠ Device movement, defined as a change by at least 1 in the number of CyPass rings visible (eg, from 1 ring to 2 rings or from 3 rings to 2 rings) that does not result in clinical sequelae (eg, secondary surgical intervention to modify device position, corneal endothelial touch by device, corneal edema leading to loss of BCDVA > 2 lines at the last postoperative visit in comparison with preoperative BCDVA, progressive endothelial cell loss, erosion of device through sclera, or device obstruction requiring secondary surgical intervention), and that is not attributable to any one or more of the following:
 - variations in gonioscopic viewing angle or illumination
 - changes in angle anatomy due to concomitant findings such as resolution of hyphema
 - changes in anterior chamber depth
 - development of focal peripheral anterior synechiae

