⁶ ECD may be requested in the fellow eye at follow-up on a case by case basis.

⁷ Visual field testing may be repeated between screening (Visit 0) and surgery (Visit 00), if needed.

⁸ UBM or OCT conducted if CyPass is not visible on Gonioscopy at two consecutive visits after Visit 3 (1 Month Follow-up). Images retained at site to demonstrate placement of CyPass.

11 Appendix B: Study Design

12 Appendix C: Data Sources

Endpoint	CRF	Comments
Primary Effectiveness Endpoint		
None		
Secondary Effectiveness Endpoints		
Mean change in IOP	Baseline: Intraocular Pressure_Glaucoma PostOp: Intraocular Pressure_Glaucoma_1	
Proportion of subjects with IOP reduction \geq 20% while using the same or fewer topical ocular hypotensive medications	Baseline: Intraocular Pressure_Glaucoma PostOp: Intraocular Pressure_Glaucoma_1 Ocular Hypotensive Medications	
Proportion of subjects who are not using ocular hypotensive medication with IOP \geq 6 mmHg and \leq 18 mmHg	Baseline: Intraocular Pressure_Glaucoma PostOp: Intraocular Pressure_Glaucoma_1 Ocular Hypotensive Medications	
Primary Safety Endpoint		
Failure to implant CyPass, defined as inability to successfully deploy or insert the CyPass.	Adverse Event(s) SX	Intraop - g) CyPass non-implantation (as defined in the protocol)

Endpoint	CRF	Comments
Clinically significant CyPass malposition, defined as CyPass positioning after deployment such that:		
The device is not in the supraciliary space, or	Adverse Event(s) SX	Postop - bb) CyPass device malposition - positioning after deployment such that the device is not in the supraciliary space (Specify)

Endpoint	CRF	Comments

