The rate of ocular SSIs associated with CyPass placement and stability	Adverse Event(s) SX	
Either of these two:
 
Postop - ee) CyPass device explantation associated with CyPass placement and stability
 
Postop - gg) Unplanned ocular surgical reintervention associated with CyPass placement and stability

Other Safety Endpoints		
Increase from baseline IOP of 10 mmHg or greater at any time at/after 30 days postoperative	Baseline: Intraocular Pressure_Glaucoma PostOp: Intraocular Pressure_Glaucoma_1	
BCDVA loss of 2 or more lines compared to screening (Visit 0)	Baseline: Visual Acuity_VAS PostOp: Visual Acuity_VAS_1	
BCDVA loss of 2 or more lines in comparison with best recorded BCDVA at any postoperative visit	Baseline: Visual Acuity_VAS PostOp: Visual Acuity_VAS_1	

Endpoint	CRF	Comments
Device movement, defined as a change by at least 1 in the number of CyPass rings visible (eg, from 1 ring to 2 rings or from 3 rings to 2 rings) that does not result in clinical sequelae (eg, secondary surgical intervention to modify device position, corneal endothelial touch by device, corneal edema leading to loss of BCDVA > 2 lines at the last postoperative visit in comparison with preoperative BCDVA, progressive endothelial cell loss, erosion of device through sclera, or device obstruction requiring secondary surgical intervention), and that is not attributable to any one or more of the following:	Adverse Event(s) SX	Postop - dd) CyPass device dislodgement or movement, without sequelae (as defined in the protocol)
variations in gonioscopic viewing angle or illumination		
changes in angle anatomy due to concomitant findings such as resolution of hyphema		
changes in anterior chamber depth		
development of focal peripheral anterior synechiae		

Endpoint	CRF	Comments
Additional Safety Assessments		
Adverse events (ocular and non-ocular)	Adverse Event(s) SX	
Device deficiencies	Device Deficiency	
Endothelial Cell Count	This will come from a dataset provided by the reading center, CIARC	
Slit lamp findings	Baseline: Slit Lamp Observations PostOp: Slit Lamp Observations_1	
Fundus examination (C/D ratio) and fundus findings	Baseline C/D: Fundus Exam PostOp C/D: Fundus Exam_1 Baseline observations: Fundus Observations PostOp observations: Fundus Observations_1	
Corneal pachymetry	Baseline: Corneal Thickness PostOp: Corneal Thickness_1	
Intraocular pressure	Baseline: Intraocular Pressure_Glaucoma PostOp: Intraocular Pressure_Glaucoma_1	

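### A stent that silently leaves the supraciliary space fits two adverse-event codes, only one reaches the primary endpoint, and no rule says which prevails

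*Protocol*

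**What the plan says.** **Primary endpoint.** Protocol 8.2.2.1 (repeated in SAP 6.2) defines clinically significant malposition by two alternatives. The first is "The device is not in the supraciliary space, or"; the second requires a clinical sequela of device position. Because they are alternatives, the first needs no sequela.

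**Adverse-event codes.** Protocol 13.1.2 item bb) is malposition, described as "positioning after deployment such that the device is not in the supraciliary space", with no sequela condition. Item dd) is "CyPass device dislodgement or movement, without sequelae". Within dd), movement is defined by a ring-count change with certain causes excluded. Dislodgement is not defined.

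**Other-safety endpoint.** Protocol 8.2.2.3 (repeated in SAP 6.4) has "Device movement, defined as a change by at least 1 in the number of CyPass rings visible", provided no clinical sequela results. It does not mention dislodgement.

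**Data sources.** SAP Section 12, Appendix C, draws both quantities from the adverse-event form. The limb of the primary endpoint about location outside the supraciliary space comes from bb). The device-movement rate comes from dd). Code dd) appears in no primary-endpoint row.

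**The concern.** The objective in Protocol 8.1 covers stability as well as placement, so late loss of position without symptoms is within what the trial set out to measure. For that event, whether the eye counts depends on which code the investigator enters. Entering bb) puts it in the primary numerator. Entering dd) alone leaves it out, unless the eye has another primary event.

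An investigator could choose dd) in good faith. Code bb) speaks of positioning after deployment, which can be read as the result of the initial placement. Dislodgement without sequelae can be read as describing a later, silent change. Nothing in either document settles this.

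The error runs one way. A primary event filed only under dd) lowers the observed rate and makes it easier to show a rate below 7%. It also mixes true losses of position into a rate meant for ring-count changes.

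**Working it through.** **Step 1: set the definitions side by side.**

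| | Primary limb (8.2.2.1) | Code bb) | Code dd) | Device movement (8.2.2.3, SAP 6.4) |
|---|---|---|---|---|
| Sequela | not needed | not needed | must be absent | must be absent |
| Refers to the supraciliary space | yes | yes | no | no |
| Excludes stents outside the space | no (it is the event) | no (it is the event) | no | no |
| Names dislodgement | no | no | yes, undefined | no |
| Role in Appendix C | primary endpoint | source for this primary limb | source for device movement only | other-safety rate |

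Take a stent that has left the space with no sequela. It meets the primary limb and bb). It also meets dd) as a dislodgement and, if the ring count changed, as a movement. The sequelae listed in 8.2.2.3 do not include location outside the space, so that endpoint does not screen the eye out either. No text gives bb) precedence, requires both codes, or checks dd) records against recorded position for primary-endpoint status.

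**Step 2: reproduce the plan's power.** Inputs: exact one-sided binomial test at 0.05 (Protocol 15.5.1.2, SAP 6.2.2); null rate 7%, assumed true rate 4% and 360 eyes (Protocol 15.8, SAP 7).

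The pass limit c is the largest integer with P(X ≤ c | n, 0.07) ≤ 0.05.

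- n = 360: P(X ≤ 17) = 0.0499 and P(X ≤ 18) = 0.0783, so c = 17 (17/360 = 4.72%).
- Power = P(X ≤ 17 | 360, 0.04) = 0.802. The stated 80% reproduces.

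SAP 6.2 uses all ITT eyes as the denominator. With the planned 450 implanted eyes (360/0.80 = 450):

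- n = 450: P(X ≤ 22) = 0.0429 and P(X ≤ 23) = 0.0649, so c = 22 (22/450 = 4.89%).

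**Step 3: eyes coded dd) alone at the boundary.** The observed count sits at c and passes. With k hidden eyes the true count is c + k, and its exact p-value is P(X ≤ c + k | n, 0.07).

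| Hidden eyes k | n = 360: true count, p | n = 450: true count, p |
|---|---|---|
| 1 | 18 (5.0%), 0.078 | 23 (5.1%), 0.065 |
| 2 | 19 (5.3%), 0.117 | 24 (5.3%), 0.094 |
| 4 | 21 (5.8%), 0.226 | 26 (5.8%), 0.179 |

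One eye is enough to turn a fail into a pass.

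**Step 4: sensitivity to an assumed share.** Let f be the share of true primary events coded dd) only. The documents give no value for f. The chance of passing at a true 7% rate is P(X ≤ c | n, 0.07(1 − f)).

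| Assumed f | n = 360 | n = 450 |
|---|---|---|
| 0 | 5.0% | 4.3% |
| 5% | 8.2% | 7.5% |
| 10% | 12.8% | 12.6% |
| 20% | 27.8% | 29.7% |

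The last row is demanding. At 7% of 450 there are 31.5 expected events, so f = 20% means about 6.3 eyes silently outside the space and coded dd) only.

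**The case against.** A reader might infer that dd) removes silent dislodgements from the primary endpoint. The documents do not support that. Code bb) states the condition almost word for word, needs no sequela, and is mapped to the primary endpoint. An investigator applying bb) as written counts the eye. Nor can dd) be called the closer match: it does not mention the supraciliary space, and the only definition it contains is a ring-count change.

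The codes are also not exclusive. The 13.1.2 list is open-ended and overlaps elsewhere, and Appendix C counts secondary surgical interventions from any of four codes. An eye may carry both bb) and dd). It is lost only if dd) is entered and bb) is omitted.

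There are partial safeguards. The visit schedule has gonioscopy at every postoperative visit and UBM or OCT when the stent is repeatedly not visible. Data are reviewed and queried (Protocol 14.2), and all adverse events are listed (SAP 6.5.1). The Manual of Procedures, which is not among the documents, may hold coding guidance.

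The shares in Step 4 are hypothetical. Failures to implant, and malpositions with a sequela, do not fit dd). The COMPASS summary (two failures to implant, eight malpositions) does not say that any was a silent loss of position.

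All of this stands as a limit on size and mechanism. It does not supply a precedence rule, and none of the safeguards is tied to classification of the primary endpoint.

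**Conclusion.** The overlap is real. Two codes fit one state, only bb) reaches the primary endpoint, and an investigator can follow the text and still leave out a primary event. What the documents show is a gap in the coding rules, not a mapping that necessarily discards events.

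The bias from this route can only lower the primary rate. Its frequency cannot be determined from the documents and may be small. The firm quantitative statement is the boundary one: a single eye coded dd) alone turns 23/450 (p = 0.065) or 18/360 (p = 0.078) into a pass. It assumes the exact test is the decision rule and, for 450, that the ITT set reaches its planned size. The Step 4 percentages rest on assumed shares and should not be read as expected inflation of the error rate. This is a cheap improvement worth making, not evidence that the primary result would be wrong.

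**What to change.** 1. State in Protocol 13.1.2 and SAP Appendix C that any stent outside the supraciliary space counts as bb) and as a primary event, with or without sequelae and whether or not dd) is also entered.
2. Limit dd) and the device-movement endpoint (Protocol 8.2.2.3, SAP 6.4) to stents still in the supraciliary space. Deleting the word dislodgement from dd) would not be enough, because 8.2.2.3 itself does not exclude a ring-count change in a stent that has left the space.
3. Before database lock, check every dd) record against the position recorded by gonioscopy, UBM or OCT. Count the eye in the primary endpoint where the stent was outside the space.

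The cost is a small data review, matching wording changes in both documents, and possibly an update to the adverse-event form. The observed primary rate may become slightly less favourable. The change concerns endpoint classification only and leaves clinical management untouched.
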